## 8.9 Duration of Study Participation

All patients must be followed for 12 months after the last dose of ruxolitinib for disease response and survival unless one of the following occurs earlier:

- consent is withdrawn
- new anti-cancer treatment is started (follow for survival only),
- patient is discharged to hospice (terminal) care (follow for survival only)

## 9 Expected Adverse Events and Potential Risks

### 9.1 Ruxolitinib

Refer to the most current IB for the comprehensive list of adverse events.

The following severe events have been seen in patients being treated for myelofibrosis or polycythemia vera and are considered expected:

Very Common (greater than or equal to 10%, or 10 or more out of 100 people)	Common (between 1 to 10%, or between 1 and 10 out of 100 people)	Rare (less than 1 out of 100 people)

• Ruxolitinib may cause low platelet counts (thrombocytopenia), low red blood cell counts

	

• Infection

• chills

• aches

• fever

	

• Progressive multifocal leukoencephalopathy

• Non-Melanoma Skin Cancer

Very Common (greater than or equal to 10%, or 10 or more out of 100 people)	Common (between 1 to 10%, or between 1 and 10 out of 100 people)	Rare (less than 1 out of 100 people)

(anemia), and low white blood cell counts (neutropenia)
 
 
• unusual bleeding
 
• bruising
 
• tiredness
 
• shortness of breath
 
• fever
 
• Cholesterol increases
 
	
 
• nausea
 
• vomiting
 
• weakness
 
• painful skin rash or blisters
 
	

The following severe events have been seen in patients being treated for acute or chronic GVHD and are considered expected.

Common for acute GVHD (1 - 10%)	Uncommon for acute GVHD (<1%)	Common for chronic GVHD (1-10%)	Uncommon for chronic GVHD (<1%)

 
• low platelet counts (thrombocytopenia), and low white blood cell counts (neutropenia); or low red cell, white cell, and platelet counts (pancytopenia)
 
• CMV infection
 
• Sepsis
 
	
 
• Septic shock
 
	
 
• low red blood cell counts (anemia)
 
	
 
• low platelet counts (thrombocytopenia)
 
• Urinary tract infection
 
• Sepsis
 
• Septic shock
 

## 9.2 Decitabine

Refer to the most current IB or package insert(s) for the comprehensive list of adverse events.

Very Common (greater than or equal to 10%, or 10 or more out of 100 people)	Common (between 1 to 10%, or between 1 and 10 out of 100 people)	Rare (less than 1 out of 100 people)

 
• low platelet count with increased risk of bruising/bleeding
 
	
 
• blurred vision
 
• pain
 
• high blood sugar
 
• headache
 
	
 
• confusion
 
• trouble sleeping
 
• fluid in the lungs
 

Very Common (greater than or equal to 10%, or 10 or more out of 100 people)	Common (between 1 to 10%, or between 1 and 10 out of 100 people)	Rare (less than 1 out of 100 people)

 
• low white blood cell count with increased risk of infection
 
• low red blood cell count (anemia) with symptoms like tiredness, low energy, or shortness of breath
 
• nausea
 
• vomiting
 
• diarrhea
 
• constipation
 
• tiredness
 
• fever
 
• pain or swelling in the arms or legs
 
	
 
• bruises or bleeding
 
• swollen lymph nodes ("glands")
 
• sores in mouth, on tongue, or on lips
 
• infection
 
• indigestion or sour stomach
 
• abnormal blood tests which suggest that the drug is affecting the liver
 
	
 
• severe allergic reaction, with symptoms like flushing, hives, trouble breathing or swallowing, dizziness, swelling of mouth or throat (while drug is being infused)
 
• serious infections
 
• death from infection, bleeding, or other cause
 

### 9.3 Risks Due to DLI

#### Acute Infusion Reaction Following Donor Lymphocytes

Although infusion of donor lymphocytes has reportedly not been associated with serious acute hypersensitivity reactions, patients will be closely watched for the occurrence of hypotension, dyspnea and angiodema during the infusion and immediately thereafter. Corticosteroids should be avoided and acetaminophen and Benadryl may be administered as needed.

#### Acute Graft-Versus-Host Disease

Infusion of donor lymphocytes into patients who relapse post allogeneic bone marrow transplantation has frequently resulted in development of acute graft-versus-host disease with involvement of the skin and liver, often requiring treatment. Despite treatment, some cases of GVHD have been of high grade and deaths from GVHD have been reported. GVHD may occur between 1 and 24 weeks post-infusion of the donor lymphocytes. Patients will have regular assessment for development of new or worsening of existing GVHD during the entire study period.

#### Bone Marrow Aplasia

After donor lymphocyte infusions, patients may develop aplasia requiring blood product transfusions and/or growth factor support. This has been reported in 10-15% of reported

cases and some patients have developed severe marrow aplasia requiring a boost or second marrow infusion. Marrow aplasia and pancytopenia may be delayed and develop between 1 and 6 months after donor lymphocyte infusions. Deaths from infection or bleeding complicating pancytopenia have been reported.

## 10 Study Agent Information

### 10.1 Ruxolitinib

[figure not shown]
#### 10.1.1 Other Names

Jakafi®

INCB018424

#### 10.1.2 Product Description

Ruxolitinib phosphate is a kinase inhibitor with the chemical name (R )-3-(4-(7H-pyrrolo[2,3-d] pyrimidin-4-yl)-1H-pyrazol-1-yl)-3-cyclopentylpropanenitrile phosphate and a molecular weight of 404.36. Ruxolitinib phosphate has the following structural formula:

Ruxolitinib phosphate is a white to off-white to light pink powder and is soluble in aqueous buffers across a pH range of 1 to 8.

Jakafi (ruxolitinib) Tablets are for oral administration. Each tablet contains ruxolitinib phosphate equivalent to 5 mg of ruxolitinib free base together with microcrystalline cellulose, lactose monohydrate, magnesium stearate, colloidal silicon dioxide, sodium starch glycolate, povidone and hydroxypropyl cellulose.

#### 10.1.3 Procurement

Incyte Corporation will supply Ruxolitinib at no charge to patients participating in this clinical trial.

Ruxolitinib will be supplied as 5 mg tablets packaged in 60-count high-density polyethylene bottles. All tablet excipients comply with the requirements of the applicable compendial monographs.

All Incyte product labels will state "Caution: New Drug--Limited by Federal (or United States) law to investigational use."

The investigator shall take responsibility for and shall take all steps to maintain appropriate records and ensure appropriate supply, storage, handling, distribution, and usage of investigational product in accordance with the protocol and any applicable laws and regulations.

#### **10.1.4 Storage Requirements**

Bottles of tablets should be stored at room temperature, 15°C to 30°C (59°F to 86°F).

#### **10.1.5 Preparation and Administration**

Tablets can be taken with or without food. Grapefruit juice should not be consumed while on Ruxolitinib.

#### **10.1.6 Drug Accountability and Destruction**

Ruxolitinib must be dispensed only from official study sites and to eligible patients under the supervision of the site investigator. Ruxolitinib should be stored in a secure area according to local regulations. It is the responsibility of the site investigator to ensure that study drug is only dispensed to patients. After final drug reconciliation, unused ruxolitinib will be disposed at the site following procedures for the disposal of anticancer drugs.

### **10.2 Decitabine**

[figure not shown]
#### **10.2.1 Other Names**

Dacogen

#### **10.2.2 Product Description**

Dacogen™ (decitabine) for Injection contains decitabine (5-aza-2'-deoxycytidine), an analogue of the natural nucleoside 2'-deoxycytidine. Decitabine is a fine, white to almost white powder with the molecular formula

of C8H12N4O4 and a molecular weight of 228.21. Its chemical name is 4-amino-1-(2- deoxy- $\beta$ -D-erythro-pentofuranosyl)-1,3,5-triazin-2(1H)-one and it has the following structural formula:

Decitabine is slightly soluble in ethanol/water (50/50), methanol/water (50/50) and methanol; sparingly soluble in water and soluble in dimethylsulfoxide (DMSO). Dacogen™ (decitabine) for Injection is a white to almost white sterile lyophilized powder supplied in a clear colorless glass vial. Each 20 mL, single dose, glass vial contains 50 mg decitabine, 68 mg monobasic potassium phosphate (potassium dihydrogen phosphate) and 11.6 mg sodium hydroxide.

#### 10.2.3 Procurement

Commercially available.

#### 10.2.4 Storage Requirements

Store vials at 25°C (77°F); excursions permitted to 15 - 30°C (59 - 86°F).

#### 10.2.5 Preparations and Administration

Decitabine is a cytotoxic drug and, as with other potentially toxic compounds, caution should be exercised when handling and preparing decitabine.

Decitabine should be aseptically reconstituted with 10 mL of Sterile Water for Injection (USP); upon reconstitution, each mL contains approximately 5.0 mg of decitabine at pH 6.7-7.3. Immediately after reconstitution, the solution

should be further diluted with 0.9% Sodium Chloride Injection, 5% Dextrose Injection, or Lactated Ringer's Injection to a final drug concentration of 0.1 - 1.0 mg/mL.

Unless used within 15 minutes of reconstitution, the diluted solution must be prepared using cold (2°C - 8°C) infusion fluids and stored at 2°C - 8°C (36°F - 46°F) for up to a maximum of 7 hours until administration.

#### **10.2.6 Stability**

Unless used within 15 minutes of reconstitution, the diluted solution must be prepared using cold (2°C - 8°C) infusion fluids and stored at 2°C - 8°C (36°F - 46°F) for up to a maximum of 7 hours until administration.

#### **10.2.7 Drug Accountability**

Decitabine is commercially available and will be procured by the inpatient pharmacy per institutional guidelines.

### **11 Clinical Evaluations and Procedures**

Scheduled evaluations up to Day +28 in each cycle may be performed +/-3 days from the targeted date; evaluations and procedures (including research related) performed after Day +28 through end of final cycle may be done +/-7 days of the targeted date. Follow-up beginning at 6 months may be done +/- 2 weeks of the targeted date. In addition, targeted days may be altered as clinically appropriate.

## 11.1 Required Clinical Care Evaluations

	Screening within 28 days of study enrollment (within 14 days of C1D1 for eligibility labs)	Every Treatment Cycle		Between study cycles (day 29-56) 	Post DLI Visit (4-6 weeks after last DLI)	Follow-Up Q 3 months from the end of last cycle through 12 months
		During Decitabine admin	Day of DLI			
Written Consent	X					
Medical history	X					
Histological confirmation of diagnosis and staging	X					
Prior treatment	X					
Physical exam	X	X 	X		X	X
Provider assessment	X	X 	X			
Weight (Height also during screen)	X	X 				
Concomitant medications	X	X (day 1 each cycle)				
Karnofsky performance status	X			X		
ECG	X			X		
Type and Screen (ABO/RH/ Indirect Antiglobulin)	X					
Assessment of AEs	X	X	X		X	
Complete Blood Count with diff (CBC)	X	X 	X	X	X	X
Comprehensive Metabolic Profile (CMP) 	X	X 	X	X	X	X
HIV test	X					
Hepatitis B and C	X					
Pregnancy test (urine or serum) for WOCBP	X 			X		
Bone Marrow biopsy	X 			X 	X	
Relapse/progression status	X			X		
Survival status						X

MT2018-07: ruxolitinib, decitabine, and DLI for post-transplant relapse of AML or MDS

	Screening within 28 days of study enrollment (within 14 days of C1D1 for eligibility labs)	Every Treatment Cycle		Between study cycles (day 29-56) 	Post DLI Visit (4-6 weeks after last DLI)	Follow-Up Q 3 months from the end of last cycle through 12 months
		During Decitabine admin	Day of DLI			
Study treatment						
Decitabine		X (day 1-10 or day 1-5 & 8-12) 				
DLI			X (between 11-21 or 13-22) 			
Ruxolitinib		2 times a day				Through 6 months post end of last cycle
Research Nurse visit		Every two weeks			X	X

CMP to include sodium, potassium, chloride, creatinine, blood urea nitrogen, and liver function tests including AST, ALT, total bilirubin, and alkaline phosphatase

For women of childbearing potential (WOCBP): urine or serum pregnancy test within 14 days prior to study registration. If a urine test is positive or cannot be confirmed as negative, a serum pregnancy test will be required.

Continuous reassessment for eligibility to proceed to subsequent cycles

Results taken out of window may be used as enrollment verification and will not be considered a deviation.

Required prior to cycle 3. This sample will not be taken if not moving on to cycle 3.

Day 1-5 in cycle 3 and 4 if CR achieved;

Between day 6 and 16 in cycle 3 and 4 if CR achieved

 Day 1 of cycle and additional frequency per site institutional guidelines for clinical care. If screening (baseline) labs were performed within 7 days of Day 1 of treatment, these do not need to be repeated. For cycle 2 and later, lab work may be performed up to 3 days prior to the day 1 treatment day.

## 11.2 Patient – Research Related

Note: if a patient is not abiding by the required clinical care calendar ([Section 11.1](#)), the collection schedule of the toxicity data and research related samples may be altered or discontinued on an individual patient basis, as appropriate.

It is recognized that with novel therapies as used in this study, the timing of protocol directed research samples may miss important patient specific events. For this reason, up to 3 extra samples for a total of 180 ml of blood may be drawn at additional time points that are not specified above.

	Prior to Cycle 1	Every Treatment Cycle	Prior to Cycle 3	Post DLI (4-6 weeks after last DLI)	90 days (+/- 7 days) after the last day of last cycle	180 days (+/- 14 days) after the last day of last cycle	Event Driven	Event Driven
		Day 1					At disease progression	At GVHD diagnosis (+7 days)
Peripheral blood: Four 10 mL heparin tubes and one 10 ml clot tube		X 		X 	X	X	X 	X
Research bone marrow aspirate samples (max 10 ml, transferred to a heparin tube)	X 		X 	X 			X 	

 Prior to decitabine and ruxolitinib administration

 Optional, Adult patients only

 This sample will not be taken if not moving on to cycle 3

 At the time of clinical biopsy. If disease progression research samples are taken prior to the post-DLI samples, additional samples are not needed

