## **8.8 Duration of Study Treatment**

The expected duration of treatment for each subject is 4 cycles of treatment, each cycle lasting 4 weeks; with up to 4 weeks of rescreening for eligibility to continue on to subsequent cycles; followed by six additional months of ruxolitinib. The following may be reasons for removal from additional study treatment:

- unacceptable toxicity
- disease progression

- new GVHD (except grade I acute GVHD)
- prolongation of the most recent cycle to more than 8 weeks (for any reason)
- inadequate cell dose for further DLI
- consent is withdrawn or patient is not compliant

Patients who are unable to receive further DLIs after initial cycle(s), may continue to receive ruxolitinib as long as the physician believes they are benefiting from the treatment, the patient has not withdrawn consent, and they have not developed unacceptable toxicity.

All patients receiving at least one cycle of treatment will be followed per [Sections 11.1](#) and [11.2](#) and be evaluable per [Section 15](#).

Patients unable to continue DLI may be treated per physician's choice. These patients will still be followed per [Sections 11.1](#) and [11.2](#).

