## **12.2 AE Documentation**

AE reporting will occur via data entry into the study eCRF. AEs reported through expedited processes (e.g., reported to Incyte, IRB, FDA, etc.) must also be reported in routine study data submissions. Patients will be monitored for adverse events after the subject has signed the ICF through 30 days after the last dose of study drug. Adverse events recorded in the eCRFs include the following:

- CTCAE grade 3 and greater allergic reactions related to ruxolitinib or decitabine occurring until 30 days after the last treatment on study
- CTCAE grades 3 and greater organ toxicity (cardiac, dermatologic, gastrointestinal, hepatic, pulmonary, renal/genitourinary, or neurologic) occurring until 30 days after the last treatment on study
- aGVHD III-IV occurring until 3 months after the last cycle of treatment
- CTCAE grade 4 neutropenia lasting more than 14 days, occurring until 30 days after the last treatment on study
- CTCAE grades 3 and greater febrile neutropenia, or grade  $\geq 3$  neutropenia with documented infection, occurring until 30 days after the last treatment on study
- CTCAE grade 4 thrombocytopenia lasting more than 14 days if pre-treatment platelet count  $> 100 \times 10^9/L$ , occurring until 30 days after the last treatment on study

In addition any event meeting the definition of a serious adverse event (SAE) regardless of attribution that occurs during this period will be documented in the source document and recorded in OnCore.

After the final treatment visit, monitoring for adverse event will become less frequent based on the schedule in [Section 11](#) and only events at least possibly related to study treatment (based on the table above) will be documented upon knowledge.

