**12.4 Early Stopping Rule Events Documentation and Reporting Requirements**

The following events count toward an early study stopping rule per [Section 15.4](#) and must be reported to the MCC Affiliate Sites Manager and to Incyte Pharmaceuticals using the Event Form found OnCore under the reports tab: grade III-IV aGVHD until 3 months after the last cycle of treatment.

An event that counts toward an early stopping rule does not necessarily constitute a SAE and should be reported as such only if they meet the criteria for reporting as defined in [Section 12.3](#).

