### **Grade III-IV aGVHD until 3 months after the last cycle of treatment**

Stopping rules were developed for excessive grade III-IV aGVHD. Previous results from trials of HMA plus DLI have reported an incidence of ~10% for aGVHD III-IV. The goal is to construct a boundary based on aGVHD grade III-IV such that the probability of early stopping is at most 5% if the true rate is equal to 10% and our sample size is 34. Given these parameters, the upper stopping boundary for aGVHD grade III-IV is 2 events out of 2 patients, 3 out of 6, 4 out of 10, 5 out of 15, 6 out of 21, 7 out of 27 or 8 out of 33. The probability of early stopping from excessive aGVHD grade III-IV if the true probability is 30% is 86%.

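### The Section 11.2 note lets sites discontinue toxicity data collection in patients off the visit calendar, against the plan's own GVHD and AE capture windows, so severe aGVHD may go uncounted

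*Combined protocol and SAP*

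**What the plan says.** All references are to the combined protocol and SAP.

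- **Section 11.2, opening note.** The trigger is "if a patient is not abiding by the required clinical care calendar". The consequence is that "the collection schedule of the toxicity data and research related samples may be altered or discontinued on an individual patient basis". The only qualifier is that this be appropriate. The note gives no criteria, no minimum data set and no exception for severe aGVHD.
- **Section 9.3.** GVHD is to be assessed regularly over the whole study, and may appear 1 to 24 weeks after an infusion.
- **Section 12.2.** AEs are monitored from consent to 30 days after the last dose. The events to be recorded include "aGVHD III-IV occurring until 3 months after the last cycle of treatment". After the final treatment visit, monitoring follows the Section 11 schedule and events are documented when they become known.
- **Sections 12.4 and 12.5.** The stopping-rule event is "grade III-IV aGVHD until 3 months after the last cycle of treatment". It must be reported, within 24 hours of the site knowing of it.
- **Section 8.8.** Patients who have received at least one cycle, and those who cannot continue DLI, are followed under Sections 11.1 and 11.2.
- **Sections 15.1, 15.2 and 15.4.** A patient is evaluable once both drugs have been started. AEs are summarised as frequencies and proportions. The stopping boundary is a count of events out of patients. None of these sections says how a patient with incomplete toxicity observation enters the count.

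**The concern.** Research samples can be dropped in a poorly adherent patient at little cost to the trial's conclusions. Toxicity data are different: grade III-IV aGVHD drives the only toxicity stopping rule. Patients who leave the visit calendar may do so because they are unwell, progressing or under care elsewhere. That is clinical reasoning rather than something the documents state, but if it is right, collection would be discontinued where severe events are most likely.

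In a count over treated patients, an event that is not ascertained lowers the numerator while the patient can remain in the denominator. The error then runs one way, towards apparent safety. It affects both the stopping rule and the descriptive AE proportions.

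**Working it through.** **1. Do the passages conflict?** Sections 9.3, 12.2 and 12.4 set assessment and capture windows with no exception for visit adherence. The Section 11.2 note permits the underlying collection to be discontinued. Section 8.8 does not resolve this, because it sends follow-up to Section 11.2, which contains the permission. Section 12.2 ties later monitoring to the Section 11 schedule, which the note allows to be altered. The reporting duty in Section 12.5 starts when the site knows of the event, so it does not oblige anyone to look.

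**2. Inputs for the stopping rule (Section 15.4).** The design target is that "the probability of early stopping is at most 5% if the true rate is equal to 10% and our sample size is 34". The boundary is "2 events out of 2 patients, 3 out of 6, 4 out of 10, 5 out of 15, 6 out of 21", then 7 out of 27 and 8 out of 33. The stated chance of stopping at a true rate of 30% is 86%.

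**3. Reproducing the plan's figures.** Let b(n) be the smallest boundary count r whose listed patient number is at least n. Let f_n(k) be the probability of k events after n patients without having stopped. Then

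f_n(k) = f_{n-1}(k)(1 - p) + f_{n-1}(k - 1)p,

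and any mass with k ≥ b(n) is moved to stopped. Running n from 1 to 34 gives:

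- p = 0.10: 4.87% (plan: at most 5%)
- p = 0.30: 86.08% (plan: 86%)

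Both agree. They assume that every event is seen.

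**4. Sensitivity to missed events.** Let m be the share of all grade III-IV aGVHD events that are never ascertained, with those patients kept in the denominator as event-free. The effective rate is p(1 - m). The documents give no value for m; the values below are assumptions.

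| m | 0.30(1 - m) | P(stop), true 30% | P(stop), true 10% | Expected number enrolled, true 30% |
|---|---|---|---|---|
| 0 | 0.300 | 86.1% | 4.9% | 16.5 |
| 5% | 0.285 | 81.8% | 4.1% | 17.8 |
| 10% | 0.270 | 76.6% | 3.4% | 19.2 |
| 20% | 0.240 | 63.9% | 2.3% | 22.2 |

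**5. The other possible handling.** Suppose off-calendar patients were instead removed from the denominator, with no events lost among the rest. If 10% are removed, 34 × 0.9 = 30.6, about 31 patients, and the chance of stopping at 30% is 82.8%. If 20% are removed, 34 × 0.8 = 27.2, about 27 patients, and it is 79.3%. The result depends on a handling rule that the plan does not give.

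**The case against.** Several objections have force.

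- **Nothing says that these patients count as event-free.** Correct. A reader might infer it from the count of events out of patients and the first-dose evaluability rule, but the plan is silent. The most that can be said is that they may be so counted.
- **Stopping treatment does not trigger the note.** Correct. A reader might infer that patients who come off treatment drop out of toxicity collection, particularly because Section 8.8 lists "consent is withdrawn or patient is not compliant" among the reasons for removal. That list concerns further study treatment, not data. Section 8.8 keeps patients who cannot continue DLI in follow-up, and Section 4 does the same for those removed for a low cell dose. The trigger is leaving the calendar.
- **Section 12 duties are not waived.** Correct for known events: severe aGVHD that comes to the site's attention must be recorded and reported. The teleconferences in Section 13.4, which cover patient updates and are set at least every 3 weeks by default, are another route to knowledge. What remains is the event nobody learns of, a narrower loss than all toxicity data.
- **The illustration is hypothetical.** Correct. An event is missed only if the patient is off calendar, collection is discontinued, severe aGVHD occurs and the site never hears of it. So m is not the share of patients missing visits and could be much smaller. A single m for all events also ignores any link between leaving the calendar and GVHD.
- **The AE consequence is limited.** AE incidence is a correlative endpoint, summarised descriptively. The grade II-IV aGVHD endpoint uses cumulative incidence, where patients lost to observation can be censored.

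None of this removes the written permission or supplies a handling rule.

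**Conclusion.** The point holds as a conflict in the text with a one-directional risk. The Section 11.2 permission cannot be squared with Sections 9.3, 12.2 and 12.4, and the passages must be reconciled. Using it could lose severe aGVHD and AE data in the direction that favours safety.

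The plan's 86% is correctly calculated for complete ascertainment. The fall to 81.8%, 76.6% or 63.9% rests on two assumptions: the share of events missed, and that the affected patients stay in the denominator. It shows sensitivity and is not an estimate of what will happen. The change is worth making because it is cheap and protects the trial's only toxicity stopping rule; the documents do not show that the rule has failed.

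A related gap is separate from the note. The Section 11.1 calendar has no GVHD row, and its AE assessment row ends at the visit 4-6 weeks after the last DLI, short of the 3-month window even for an adherent patient.

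**What to change.** 1. In the Section 11.2 note, remove toxicity data from its scope so that the flexibility applies to research samples only.
2. State that AE, SAE and aGVHD collection under Sections 12.2 to 12.4 continues for its full window in every treated patient, whatever the visit adherence, using outside records or telephone contact where visits are missed, unless consent for follow-up is withdrawn.
3. Whenever the stopping rule is assessed, report the number of patients incompletely observed for grade III-IV aGVHD. It would help to state in Section 15.4 how those patients enter the denominator, and in Section 15.2 how they enter the AE proportions.

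The cost is a few sentences of text and a little coordinator effort to obtain outside records. No visits or procedures are added.
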